--	--

- Update information on social history since screening.
- Abbreviated physical examination (pre-dose).
- Vital signs.
- Blood sampling for determination of the following parameters:
 - CBC and biochemistry;
 - MetHb%; and
 - PK analysis for tafenoquine.
- Urine sampling for determination of the following parameters:
 - Urine pregnancy test (β -HCG) (pre-dose, WOCBP participants only);
 - Urinalysis (specific gravity, power of hydrogen [pH], glucose, protein, blood, ketones, leukocyte esterase, and nitrites). Microscopic examination (if blood, leukocyte esterase or nitrites are positive); and
 - Urine drug screen (amphetamines, methamphetamines, barbiturates, benzodiazepines, cocaine, methadone, opiates, phencyclidine, tetrahydrocannabinols, and tricyclic antidepressants).
- Alcohol breath test.
- Psychiatric Assessments
 - DHI (only collected if participant reports AE of dizziness or vertigo); and
 - LSEQ assessment.
- Recording AEs and any concomitant medications;
- Inclusion/exclusion criteria confirmed,
- Randomize subject using IWRS using clinical site as a randomization variable; and
- Dispense IMP and provide instructions on use of diary card and training on electronic compliance system.

Part 1 - Treatment Phase, Week 4 to Week 52 (Visits 3, 4, 5, and 6):

- Abbreviated physical examination for Weeks 4, 12 and 24
- Vital signs.
- 12-lead ECG (Weeks 4 and 52 [Visits 3 and 6]).
- Blood sampling for determination of the following parameters:
 - CBC and biochemistry;
 - MetHb %; and
 - PK blood collection for tafenoquine.
- Urine sampling for determination of the following parameters:
 - β -HCG urine screen (WOCBP only);
 - Urinalysis (specific gravity, pH, glucose, protein, blood, ketones, leukocyte esterase, and nitrites). Microscopic examination (if blood, leukocyte esterase or nitrites are positive); and
 - Urine drug screen (amphetamines, methamphetamines, barbiturates, benzodiazepines, cocaine, methadone, opiates, phencyclidine, tetrahydrocannabinols, and tricyclic antidepressants).
- Ophthalmic Assessments (before pupil dilation):
 - BCVA (ETDRS letter score);
 - Color vision assessment with FM-100 hue test;
 - Mars letter contrast sensitivity test;
 - M-chart distortion test; and

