In Study 057, 10 (14.3%) participants in the tafenoquine Recommended Regimen group and 7 (21.9%) participants in the placebo group had evidence of corneal deposits in either eye at screening. After the screening visit, 15 (21.4%) participants receiving tafenoquine and 4 (12.5%) participants receiving placebo developed new-onset corneal deposits in one or both eyes during the study. Approximately 60% of the corneal deposit cases among participants receiving tafenoquine and 100% of the cases among participants receiving placebo emerged by Week 12 of the study. No trends were apparent with respect to the time to onset of these new corneal deposits in participants who did not have corneal abnormalities at screening. New-onset corneal deposits in all four participants in the placebo group resolved within 6 weeks of onset, while in the tafenoquine Recommended Regimen group, corneal deposits resolved within 12 weeks of onset in all but one participant. Corneal deposits in the remaining tafenoquine-treated participant resolved by Week 48.

In summary, benign, reversible corneal deposits have been noted in some participants treated with the tafenoquine Recommended Regimen. Participants are unaware of the development of these corneal deposits; it does not impact vision, and resolves within 1 year in all cases.

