5.2.2. Secondary Endpoints

- The incidence, severity and relationship to the IMP of AEs (including unexpected toxicities, AEs encountered during or after IMP administration), safety laboratory parameters, vital signs, and ECG up to and including the end of treatment period Week 52 (Visit 6).
- Mean change from baseline in key SD-OCT parameters including CST, TMV, parafoveal (inner ring of ETDRS grid) retinal thickness and the proportion of participants ellipsoid and interdigitating zone disruption (as per [Table 5](#)).
- Proportion of participants with abnormal changes from baseline observed on qFAF using the Spectralis HRA+OCT device with grey scale values extracted from these images for statistical analysis using qFAF software (Heidelberg Engineering).
- Mean change from baseline in BCVA.
- Proportion of participants with corneal deposits from slit lamp examination of the corneal epithelium.
- Time to onset of corneal deposits and overall time duration to resolution post treatment start.
- Time duration to resolution of corneal deposits after treatment cessation.
- Proportion of participants with new abnormalities compared with baseline observed with color retinal digital photography (conventional and wide field).
- Proportion of participants with new abnormalities compared with baseline observed with microperimetry.
- Proportion of participants with any new anomaly on the backlit ETDRS chart.
- Proportion of participants with any clinically significant change in ETDRS BCVA (defined as ≥ 15 letter change [≥ 3 lines] of change in ETDRS BCVA at 4 meters)
- Proportion of participants who develop a color deficiency using the FM-100 hue test.
- Proportion of participants who develop a loss of 0.12 or greater logCS on the Mars letter contrast sensitivity test.

- Proportion of participants who develop a psychiatric disorder in accordance with the DSM-5 as assessed with the M.I.N.I. 7.0.2 assessment questionnaire and suicidal ideation or suicide attempt by C-SSRS interview.
- Proportion of participants with an AE of dizziness or vertigo and severity as assessed by the DHI.
- Mean change from baseline in GTS, QOS, AFS, and BFW as assessed by the LSEQ.

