After completion of the assessments and after administration of the tafenoquine dose, participants will be allowed to leave the Study Site if they are considered to be in good health by the investigator.

8.3. Treatment Period: Week 4, 12, 24, and 52 (Visits 3, 4, 5 and 6)

Participants will report to the Study Site in the morning.

The following assessments will be performed over the treatment period:

- Abbreviated physical examination- a symptom-directed physical examination will be performed based on signs and symptom the participant has reported verbally. A symptom-directed physical examination may also be performed if it is required according to the opinion of the investigator.
- Vital signs (blood pressure, pulse rate, respiratory rate and sublingual body temperature).
- 12-lead ECG (Week 4 and 52).
- Blood sampling for determination of the following parameters:
 - CBC;
 - Biochemistry;
 - MethHb %;
 - Plasma for PK analysis;
- Urine sampling for determination of the following parameters:
 - Urine β -HCG pregnancy test (WOCBP only) at Weeks 4, 12, 24 and 52;
 - Routine urinalysis (dipstick and urine microscopy if blood, leukocyte esterase, or nitrites are positive); and
 - Urine drug screen (amphetamines, methamphetamines, barbiturates, benzodiazepines, cocaine, methadone, opiates, phencyclidine, tetrahydrocannabinols, and tricyclic antidepressants);

Ophthalmic Assessments: The following ophthalmic tests will be performed routinely during the Treatment Period at Weeks 12, 24 and 52 Ophthalmic assessments may be scheduled as a second visit during weeks when most of the examinations are performed to not overburden the length of the visit for subjects.

Before pupil dilation:

- BCVA (ETDRS letter score);
- Color vision assessment with FM-100 hue test;
- Mars letter contrast sensitivity test;

- M-chart distortion test; and
- Slit lamp examination and corneal deposit grading (the Orlando system).

After pupil dilation:

- MAIA Microperimetry (only Weeks 24 and 52);
- Heidelberg Spectralis SD-OCT (including wide field macula scan);
- Heidelberg Spectralis qFAF (set of 3 images to ensure consistency in measurement);
- Digital photograph of corneal surface (conventional and wide field);
- Digital photograph of retina (conventional and wide field);
- Slit lamp retinal examination and IOP measurement; and
- **Psychiatric Assessments**
 - M.I.N.I. English Version 7.0.2;
 - DHI (only if a participant reports AE of dizziness or vertigo); and
 - LSEQ.

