9.2.6. Ophthalmic Assessments

The ophthalmic assessments will be conducted at Screening at (Visit 1b or 1a depending on site and subject preference) and repeated at Weeks 12, 24, and 52 of the Treatment Phase and at the EOS visit (Week 64). Ophthalmic assessments will be repeated at Week 76 (Visit 8) and quarterly thereafter to 12 months if ongoing or new ophthalmic abnormalities are identified at the Week 64 visit. Microperimetry testing will be conducted at Screening twice with the first result discarded to minimize learning effect and at Weeks 24, 52 and 64. Non-clinically significant abnormalities at Baseline (Week 1, Day 1) will be recorded as medical history and will only be followed up after Week 64 if the abnormality worsens during the Treatment Period.

Please note, only tests that are abnormal at the Week 64 visit will be followed up in Weeks 76, 89 or 104 (Visits 8, 9, or 10). For example, if corneal deposit was the only abnormality found during Week 64, then there is no need to repeat any of the ocular examinations except for corneal photography and corneal slit lamp examination at Weeks 76, 89 or 104. Therefore, not all ophthalmic testing will need to be completed in Phase 3 of the study at the discretion of the PI.

Specific test parameters will be provided in the ophthalmology manual for the study.

Routine ophthalmic tests will include the following:

- BCVA (ETDRS);
- Color vision assessment with FM-100 hue test. The Lanthony D15 test will be administered immediately prior to the FM-100 test to reduce learning affects.
- Mars letter contrast sensitivity test;
- M-chart;
- Slit lamp examination of anterior and posterior segment
- Intraocular pressure measurement
- Microperimetry (Weeks 24, 52 and 64).

- SD-OCT (including wide field macula scan);
- qFAF (set of 3 images to ensure consistency in measurement);
- Digital photograph of corneal surface (conventional and wide field); and,
- Digital photograph of retina (conventional and wide field)

Abnormal results may be further investigated using microperimetry, FM-100 hue test, Mars contrast sensitivity letter reading test, M-chart, slit lamp examination, SD-OCT (including wide field macula scan) and qFAF depending on the nature of the abnormality.

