12.2.3.2. Secondary Endpoints

The incidence of AEs, SAEs, laboratory parameters and vital signs will be summarized descriptively by treatment group and study visit. The AEs will be summarized at $\geq 1\%$ (common) and $\geq 10\%$ (very common) level.

For the secondary safety endpoints, the proportion of participants with an abnormal change or new abnormal change will be compared by a Fisher's exact test between tafenoquine and placebo. The 95% CI of the abnormality rate will be summarized by Clopper Pearson Exact methodology. A logistic regression will be used to compare the risk of having the abnormality (odds ratio and 95% CI) between tafenoquine and placebo. These analysis methods will be applied to the following secondary safety endpoints: proportion of participants with abnormal changes from baseline observed on qFAF, proportion of participants with corneal deposits from slit lamp examination of the corneal epithelium, proportion of participants with new abnormal changes from baseline observed with color retinal digital photography (conventional and wide field), proportion of participants with new abnormal changes from baseline observed with microperimetry, proportion of participants with any new anomaly on the backlit ETDRS chart, proportion of participants with any clinically significant change in ETDRS BCVA (defined as ≥ 15 letter change [≥ 3 lines] of change in ETDRS BCVA at 4 meters), proportion of participants who develop a new color deficiency using the FM-100 hue test, proportion of participants who develop a loss of 0.12 or greater logCS on the Mars letter contrast sensitivity test, proportion of participants who develop a new identified psychiatric disorder, and proportion of participants with an AE of dizziness or vertigo and severity as assessed by the DHI.

For time to event safety endpoint, a log-rank test will be used to compare the time to onset/resolution of the event between tafenoquine and placebo. Cox regression will be used to compare the risk of having the safety endpoint (hazard ratio and 95% CI) between tafenoquine and placebo. The survival analysis methods will be applied to the endpoints of time to onset, and time to resolution of corneal deposits after treatment cessation.

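### Onset and post-treatment resolution of corneal deposits are known only to within the gaps between slit-lamp visits, yet Section 12.2.3.2 names only ordinary log-rank and Cox methods

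*Combined protocol and SAP*

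**What the plan says.** - **Endpoints.** Section 5.2.2 lists "Time to onset of corneal deposits and overall time duration to resolution post treatment start", and separately the time to resolution after treatment ends.
- **Methods.** Section 12.2.3.2 states that "a log-rank test will be used to compare the time to onset/resolution of the event between tafenoquine and placebo", with Cox regression for the hazard ratio. It then specifies: "The survival analysis methods will be applied to the endpoints of time to onset, and time to resolution of corneal deposits after treatment cessation". Duration counted from treatment start is not named there and falls only under the general time-to-event sentence. No interval-censored method, rule for dating onset or resolution, or handling of ties is given.
- **Visits.** Section 8.3 says: "The following ophthalmic tests will be performed routinely during the Treatment Period at Weeks 12, 24 and 52". Section 9.2.6 and the schedule of events agree and add Week 64. Weeks 76, 89 and 104 follow only if the Week 64 examination is abnormal. Windows from Week 12 onward are plus or minus 2 weeks.
- **Synopsis.** The assessment block headed "Part 1 - Treatment Phase, Week 4 to Week 52 (Visits 3, 4, 5, and 6" lists the slit lamp with no restriction to named weeks, although it restricts ECG, microperimetry and the M.I.N.I. Read literally, it includes Week 4, which the schedule, 8.3 and 9.2.6 omit.
- **Background.** Section 2.1.1.1 says participants are unaware of the deposits. In Study 057, new deposits on placebo (4 cases) all cleared within 6 weeks. On tafenoquine (15 cases), "corneal deposits resolved within 12 weeks of onset in all but one participant", and that one cleared by Week 48. In Study 033, 69 of 74 tafenoquine participants in the subgroup had deposits at the end of dosing. Of these, 42 of 69 had cleared 3 months later and the rest within a year.

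**The concern.** An ordinary log-rank test and Cox model take each event time as known. Here no symptom prompts an extra visit, so a first positive slit lamp shows only that onset fell somewhere since the last clear one. A first clear slit lamp bounds resolution in the same way. If visit dates are entered as event times, reported medians are visit weeks and the data are heavily tied.

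An episode that begins and ends between two visits leaves no trace. If episodes are shorter in one arm, more of them are lost in that arm, and the onset hazard ratio then mixes frequency with duration. Corneal deposits are the known eye effect of tafenoquine (8.2% against 0% on placebo in Table 1), so figures for onset and duration are likely to be quoted.

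**Working it through.** The plan states no event count, power or precision for the corneal endpoints, so there is no figure of its own to reproduce. The check starts from the visit schedule.

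**1. Gaps.** On treatment: 12 − 0 = 12, 24 − 12 = 12, 52 − 24 = 28 weeks. After cessation: 64 − 52 = 12, 76 − 64 = 12, 89 − 76 = 13, 104 − 89 = 15 weeks. With 2 weeks either way at both ends, a 12-week gap between visits can run from 8 to 16 weeks and the 28-week gap from 24 to 32. On treatment, onset can take only three nominal values.

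**2. Lateness for persistent deposits.** If onset is uniform within a gap G, the mean delay to the next visit is G/2: 12/2 = 6 weeks and 28/2 = 14 weeks. On the same assumption, resolution after cessation is dated late by 12/2 = 6 to 15/2 = 7.5 weeks. If Study 033's pattern recurred, about 42/69 = 61% of resolutions would be recorded at the single Week 64 visit.

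**3. Chance of being seen.** For an episode of length d with uniform onset, P(seen) = min(1, d/G). The durations tried are Study 057's upper figures.

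| Duration | 12-week gap | Week 24–52 gap | Onsets spread over Weeks 0–52 |
|---|---|---|---|
| 12 weeks | 100% | 12/28 = 43% | (12+12+12)/52 = 69% |
| 6 weeks | 6/12 = 50% | 6/28 = 21% | (6+6+6)/52 = 35% |

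**4. Recorded duration.** Suppose duration ran from first positive to first clear visit. Episodes of 6 or of 12 weeks that are seen are equally likely to be seen first at Week 12, 24 or 52, and the following gaps are 12, 28 and 12 weeks. Both true durations then give a recorded mean of (12 + 28 + 12)/3 = 17.3 weeks, so the record cannot tell them apart. As bounds, a deposit seen only at Week 24 lasted between 0 and 52 − 12 = 40 weeks.

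**5. Onset hazard ratio.** Assume constant onset hazards matching Study 057's 21.4% (15/70) and 12.5% (4/32) by Week 24, and one episode per person.

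- Hazards: −ln(1 − 15/70)/24 = 0.01005 and −ln(1 − 4/32)/24 = 0.00556 per week. True ratio 1.81.
- Tafenoquine, 12-week episodes: onsets in Weeks 0–24 or 40–52 are seen, 0.214 + 0.076 = 0.290.
- Placebo, 6-week episodes: onsets in Weeks 6–12, 18–24 or 46–52 are seen, 0.032 + 0.030 + 0.025 = 0.087.
- Ratio of cumulative hazards of first detection: −ln(1 − 0.290) / −ln(1 − 0.087) = 0.343/0.091 = 3.8.
- Placebo hazard in both arms, durations still 12 and 6 weeks: 0.177 against 0.087 detected, ratio 0.194/0.091 = 2.1.
- Persistent deposits: every onset is eventually seen and the ratio stays at 1.81.

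Simulations with 300 per arm and visits at Weeks 12, 24 and 52 agree. The ranges are across separate runs.

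| Scenario | Cox on visit dates | Grouped-time proportional hazards |
|---|---|---|
| True 1.8, durations 12 and 6 weeks | 3.7–3.9 | 3.7–3.8 |
| Equal hazards, durations 12 and 6 weeks | 2.2 (92% reject) | 2.1–2.2 (92% reject) |
| True 1.8, persistent deposits | 1.83–1.86 | 1.81–1.83 |

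In the persistent case, Cox on exact times gave 1.86 in the run where it was fitted, matching Cox on visit dates. With equal hazards and equal durations, Cox on visit dates rejected in about 5% of runs. The interval-censored type of model therefore changes how times are described, and hardly changes the treatment comparison.

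**The case against.** The best defence is that both arms share one schedule, so coarse dating alone does not invalidate the comparison. That stands: type I error holds when durations are equal, and Cox on visit dates is unbiased when deposits persist. A reader might infer that the planned test will produce a false difference between arms. The documents do not support that. It needs durations that differ by arm, and the evidence is 15 and 4 cases whose 12 and 6 weeks are upper limits. All 4 placebo cases also emerged by Week 12, so the 21% detection figure for the Week 24–52 gap matches no observed placebo case. Study 033, the larger tafenoquine series, had 27 of 69 (39%) unresolved 3 months after dosing, which points to persistence.

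Further points on that side also stand:

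- It is tempting to say the plan dates onset at the first positive visit. No rule is stated; this is only what ordinary methods would imply.
- Sections 12 and 12.2.1 defer detail to a later SAP that is not in the reviewed text and could supply a rule. Section 12.2.3.2 nevertheless already commits to specific methods.
- The 28-week gap does not bear on resolution after cessation.
- The synopsis already plans to tabulate deposit grades at each time point, and Section 12.2.3.2 compares the proportion with deposits by Fisher's exact test and logistic regression.
- A reader might expect interval censoring to cure the hazard ratio. Step 5 shows it does not, because a clear visit does not exclude an earlier episode that has gone.
- The endpoint is secondary, and the protocol describes the deposits as benign and reversible.

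**Conclusion.** The point holds as a matter of dating and reporting. With these visits, onset on treatment is observable only within 12, 12 and 28 weeks, and resolution after cessation only within 12 to 15 weeks. Treated as exact, onset of persistent deposits is late by a mean of about 6 or 14 weeks, assuming uniform onset within a gap. These limits follow from the schedule and from deposits going unnoticed; they do not depend on how long deposits last.

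Distortion of the onset hazard ratio is conditional. It could be about twofold (3.8 against 1.8) if Study 057's upper durations applied in each arm, and absent if deposits persist as Study 033 suggests. The documents do not settle which case applies, and no analysis of these visits recovers episodes that fell wholly between them. The primary endpoint is unaffected. This is a cheap improvement.

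**What to change.** In Section 12.2.3.2, or in the SAP that implements it:

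- Analyse time to onset and time to resolution after cessation as interval-censored, using the last visit without the event and the first visit with it. Give a Turnbull estimate and an interval-censored or grouped-time proportional hazards comparison.
- Report duration, including duration from treatment start, as minimum and maximum bounds.
- State that this corrects the dating of observed deposits but not bias from episodes missed between visits if durations differ by arm. Describe the onset hazard ratio as referring to the first detected deposit, and present it beside the by-visit proportions the synopsis already plans.
- Reconcile the synopsis block with the schedule, 8.3 and 9.2.6 on whether a Week 4 slit lamp is done, since this sets the first interval (12 weeks, or 4 and 8).

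The cost is SAP wording and a standard procedure. Reported medians become ranges and look less precise. No visit is added.

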5.3. Rationale of Dose Selection and Dosing Regimen

Previous clinical studies support a Recommended Regimen for malaria prophylaxis of a loading dose of 200 mg once daily for 3 days before travel to a malarious area, followed by weekly 200 mg maintenance doses while in the malarious area and an additional dose of 200 mg at one week of return from travel.

The tafenoquine dose regimen chosen for this study is based on safety and tolerability data, PK data from Phase 1 and 2 studies and efficacy data from dose-ranging chemoprophylaxis studies. The tafenoquine 200 mg dose is regarded as the highest, well-tolerated dose that achieves a protective tafenoquine concentration of 80 ng/mL in 95% of the sample population. Moreover, this is the tafenoquine recommended regimen for malaria prophylaxis approved by the FDA. Results from the placebo arm will be used as a comparator for spontaneous occurrence of ophthalmic and psychiatric effects.

5.4. Individual Subject Withdrawal

All efforts will be made to retain participants through to study completion. Participants may be withdrawn from the study for any of the following reasons: 1) withdrawal of consent, 2) lost to follow-up, 3) evidence of substance abuse that may affect the participant's capacity to complete the study in the investigator's opinion and 4) development of a new or worsening psychiatric disease (including suicidal ideation) at a non-scheduled visit or during routine M.I.N.I. evaluation or reported at an unscheduled visit that would jeopardize the safety of the participant if they continued in the study (see [Section 9.2.7](#)).

Participants will be considered withdrawn if they state an intention to withdraw, fail to return for visits, or are lost to follow-up for any other reason. The investigator will make every effort to determine the primary reason for a participant's withdrawal from the study and record this information in the eCRF. For participants who are lost to follow-up, the investigator will demonstrate "due diligence" by documenting all steps taken to contact the participant (e.g., dates of telephone calls) in the source documents.

Unless lost to follow-up, withdrawn participants will be asked to participate in a safety visit as soon as possible after the time that withdrawal has been requested or determined to be in the best interest of the subject and return for a final safety visit 65-75 days after the last dose of tafenoquine (after 5 half-lives tafenoquine clearance). The date of withdrawal in the case of lost to follow-up is the date of the last contact with the subject either in the clinic or by telephone. The date of withdrawal for a subject who withdraws consent is to be reported on the Disposition eCRF as the date of withdrawal; however, if the subject agrees to safety follow-ups, the date of last contact with the subject, as described above, will also be recorded on the eCRF. See [section 8.4](#) for a list of procedures to be conducted at this visit. The reason for treatment discontinuation will be documented on the Drug Compliance eCRF.

